12.1 Statistical analysis plan

The primary analysis will be conducted at least 6 months after the last patient is enrolled. Cox proportional hazards regression will be used to estimate hazard ratios comparing PFS for tamoxifen plus palbociclib and fulvestrant plus palbociclib. Fulvestrant will be considered promising for the unselected population if the fitted hazard ratio is < 0.8 , and for the ESR1-mut subpopulation if the hazard ratio is < 0.65 .

Response rate will be compared between treatment arms using the mid-P correction to Fisher's exact test for univariate comparisons, and logistic regression for exploratory multivariable models. Cox proportional hazards regression will be used for analyses with overall survival as the endpoint.

Adverse events will be reported for all patients in the safety cohort defined above, summarized by treatment group. Adverse events and serious adverse events will be tabulated in order of prevalence, with the highest grade reported by each patient.

Concordance of ESR1 status in plasma and biopsy samples will be assessed primarily by agreement regarding presence/absence of mutations for tissue and blood samples collected no more than 30 days apart and without intervening therapy. Kappa statistics adjusted for clustering (both pre-therapy and post-therapy time points for some subjects) will describe basic agreement. Additionally, between-subject and within-subject variation in mutant allele frequency will be compared using linear mixed models and the concordance correlation coefficient. This approach (complementary **analysis of categorical and continuous versions of**

ESR1 mutation status) may also be applied to assessment of within-patient longitudinal change. The primary analysis for these correlative studies will examine presence and allele frequency of any ESR1 mutation. Secondary analyses will examine and compare tissue-blood concordance and longitudinal change in liquid biopsy measures for specific ESR1 mutations. Level and change in circulating levels of ESR1-mt will be assessed as predictors of PFS using Cox proportional hazards regression with time-varying covariates. All hypothesis tests will be two-sided.

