1.1 Background

A major challenge is to identify the drivers of progression from primary to metastatic breast cancer, and identify new targets for treatment. Mutations in the estrogen receptor (ESR1) are a potential resistance mechanism to endocrine therapy (1-9). In cell based-models, the presence of a mutation in ESR1 confers constitutive and ligand independent activity.(3) Although these mutations are extremely rare in previously untreated patients with early breast cancer, the development of these mutations over time after exposure to hormonal therapy with tamoxifen or AIs has been recently demonstrated to occur in as many as 14-54% of patients with estrogen receptor- positive (ER+) metastatic breast cancer (MBC).(7)

The mutations primarily occur in the ligand binding domain (LBD) of ESR-1 and there have been at least 6 mutations described. A recent study by Chandarlapathy identified additional (albeit very rare) ESR1 mutations (10) Patients whose tumors harbor *ESR1* mutations have poor overall survival. In a recent large meta-analysis including data from 1540 patients, 28% had ESR mutations and had significantly worse PFS. The presence of ESR1 mutation, however, did not predict outcome on fulvestrant based therapy. (11) Even using a small cohort of patients, we reported shorter progression free survival (PFS) in patients with endocrine-resistant ER+ breast cancer receiving palbociclib who had *ESR1* mutations detected in cfDNA (12)

Together these observations support the tenable hypothesis that these mutations are clinically significant and the tumors that harbor them are strongly dependent upon ESR1 signaling.

Interestingly, in vitro, both tamoxifen and fulvestrant appear to have activity in the setting of ESR1 mutations; although different ESR1 mutations appear to have varying thresholds for effective dosing of both agents that define their level of partial resistance (3). Our group has recently performed detailed analysis of drug response in genome-edited T47D and MCF-7 cells, and these data were published Bahreini et al (13) Briefly, we introduced the most

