3. STUDY PLAN AND PROCEDURES

3.1 Overall study design and flow chart

Patients with ER+ breast cancer who had 1 to 3 prior lines of endocrine therapy and up to one line of chemotherapy for MBC, excluding fulvestrant and tamoxifen, will be randomized in a 1:1 ratio to receive fulvestrant 500mg IM Q28 days with one extra dose on D15 of the first cycle (as a loading dose) plus palbociclib 125mg/day PO on a 21 days on/7 days off schedule or tamoxifen 20mg PO daily plus palbociclib 125mg/day PO on a 21 days on/7 days off schedule. Patient accrual will be a goal of 40 evaluable at up to 4 sites. At randomization, plasma will

be obtained for evaluation of ESR1-mt and a biopsy will be obtained when possible. During treatment, all patients will undergo ct-DNA ESR1 mutation evaluation every 28 days. Treatment will continue until disease progression or unacceptable toxicity. At the time of disease progression, a second biopsy will be obtained when possible and the last blood drawn for evaluation of ct-DNA ESR1-mt will occur. All tissue obtained will also undergo molecular analysis to determine the activity of mutant ESR1.

[figure not shown]

FIGURE 5. Study Schema

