5.1.2 Patient Randomization

A member of the study team will confirm eligibility criteria and complete the protocol - specific eligibility checklist. Registration must occur prior to the initiation of therapy. Any participant not registered to the protocol before treatment begins will be considered ineligible and registration will be denied.

The Coordinating Center (UPMC Hillman Cancer Center) will review the submitted documents in order to verify eligibility and consent. To complete the registration process, the Coordinating Center will:

1. Register the participant on the study with the UPMC Clinical Research Services Coordinating Center (CRSCC).
2. Upon confirmation of registration, the Coordinating Center will provide the study specific participant case number, and assigned treatment arm to the participating institution.

Following registration, participants may begin protocol treatment and must begin treatment within 5 to 7 days. Issues that would cause treatment delays should be discussed with the Principal Investigator. If a participant does not receive protocol therapy 5 to 7 days following

registration, the participant's protocol status must be changed and the occurrence must be communicated to the UPMC CRSCC of participant status changes as soon as possible.

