12.2 Sample size justification

The study sample size is restricted by external constraints: a planned study with a PFS endpoint powered to direct future therapy choices failed to accrue, in part because of the ever-shifting treatment landscape as described above. A study with n=40, 20 each receiving fulvestrant plus palbociclib or tamoxifen plus palbociclib, will allow sufficient exploration of a variety of study aims, in order to prioritize and inform the aims of future studies. If a sufficient number of accrued patients have ESR1-mt disease, it may be feasible to evaluate the association between mutational burden and response to continued endocrine+palbociclib therapy. Alternatively, there may be a strong signal for evolution of mutational frequency as different for patients receiving fulvestrant+palbociclib versus tamoxifen+palbociclib. Similarly, there may be a signal suggesting that continued endocrine+palbociclib therapy is associated with clinical benefit only in patients with ESR1-mt tumors who receive fulvestrant+palbociclib

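### The PFS hazard ratio behind the unselected 0.8 rule has no stated adjustment for baseline ESR1 status, so a chance ESR1 imbalance shifts it; stratifying on data already collected removes that shift at small cost

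*Combined protocol and SAP*

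**What the plan says.** - **PFS model (12.1).** "Cox proportional hazards regression will be used to estimate hazard ratios comparing PFS for tamoxifen plus palbociclib and fulvestrant plus palbociclib". No covariate or stratum is named. Multivariable models are mentioned only for response rate, as exploratory.
- **Decision rule (12.1).** "Fulvestrant will be considered promising for the unselected population if the fitted hazard ratio is < 0.8", and separately "for the ESR1-mut subpopulation if the hazard ratio is < 0.65". Both are cuts on a point estimate, with no interval.
- **Allocation (3.1, 5.1.2, 12.2).** Patients "will be randomized in a 1:1 ratio to receive fulvestrant 500mg IM Q28 days" or the tamoxifen regimen, and "the Coordinating Center will provide the study specific participant case number, and assigned treatment arm to the participating institution". No stratification factor is stated. The size is given as "A study with n=40, 20 each receiving fulvestrant plus palbociclib or tamoxifen plus palbociclib".
- **Prognosis (1.1).** "In a recent large meta-analysis including data from 1540 patients, 28% had ESR mutations and had significantly worse PFS". The authors' own small palbociclib cohort also showed shorter PFS with the mutation. The same section adds that ESR1 mutation did not predict outcome on fulvestrant-based treatment. No hazard ratio is given for any of this.
- **Data available (3.1, Table 4 in 9.1).** Plasma for ESR1 is drawn from all patients before treatment and every 28 days on treatment.
- **Other use of ESR1 (12.1).** The level and change of circulating mutation enter a Cox model as time-varying predictors of PFS. That model is not described as adjusting the arm comparison.
- **Status (11.1).** PFS is a secondary endpoint; the primary objectives are descriptive.

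**The concern.** With 20 patients per arm, a prognostic marker carried by about a quarter of them can easily fall unevenly. An arm-only Cox model then attributes part of the marker's effect to treatment, in whichever direction the split happened to go. Because the label is a cut at 0.8 on the fitted value, such a shift can decide it. ESR1 is the factor the trial is built around, and it is already measured in everyone before treatment.

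At stake is how the team reads the one split it will actually observe. Section 12.2 says the results are meant to prioritize later studies. The trial is open label, so deciding whether to adjust after the split and outcomes are known would be a data-driven choice.

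**Working it through.** The plan gives no alpha, power, event count or design HR for PFS, so it has no figure of its own to reproduce. The check is therefore of chance imbalance and its consequence.

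**Inputs from the documents.** 40 patients, 20 per arm (12.2); plasma mutation prevalence 25%, or 10 of 40 (6.3.5); cut at HR 0.8 and at least 6 months' follow-up after the last enrolment (12.1).

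**Assumptions, not in the documents.** Prognostic HR *g* of 1.5 to 3; exponential PFS; wild-type median 5 months with 18 months' accrual, or 6 months with 24 months' accrual. Either gives about 34-35 events.

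**1. Chance of an uneven split.** With *k* mutant patients on fulvestrant, P(k) = C(10,k)·C(30,20−k)/C(40,20).

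- P(k ≤ 3) = 0.0002 + 0.0040 + 0.0282 + 0.1043 = 0.1367. Either direction: 2 × 0.1367 = **0.273**.
- 8:2 or worse: 2 × (0.0002 + 0.0040 + 0.0282) = 0.065.
- With 11 mutant patients (28% of 40), a difference of 5 or more has probability 0.155.

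**2. Rough size of the shift.** With no treatment effect and an equal prognostic effect in both arms, the unadjusted HR is about exp[(p_F − p_T)·ln g], where p is the mutant proportion in each arm. For 3/20 against 7/20 this is exp(−0.20·ln g): 0.92, 0.87 and 0.80 for g = 1.5, 2 and 3.

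**3. Simulation, no treatment effect, equal prognostic effect.** Ranges cover both sets of assumptions; with 4,000 runs the Monte Carlo SE of a proportion near 40% is √(0.4·0.6/4000), about 0.8 points.

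| g | Median unadjusted HR, 3 F : 7 T | P(HR < 0.8), 3 F : 7 T | P(HR < 0.8), 7 F : 3 T |
|---|---|---|---|
| 1.5 | 0.92-0.93 | 34% | 18-21% |
| 2 | 0.88 | 38-39% | 15-16% |
| 2.5 | 0.86 | 42% | not tabulated |
| 3 | 0.84-0.85 | 43-44% | 11% |

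With baseline ESR1 as a stratum or covariate, the median HR is about 1.00 and P(HR < 0.8) is 26-29% at each of these splits. With a wild-type median of 11 months (28 events, g = 2), the 3:7 split gives 0.87 and 41% unadjusted, against 30% stratified.

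**4. Averaged over all splits.** From event count alone, P(HR < 0.8 given HR = 1) = Φ(ln 0.8/√(4/events)). With 34 events this is Φ(−0.223/0.343) = Φ(−0.65) = 0.26; it runs from 29% at 24 events to 24% at 40. The simulated average at g = 2 is 26% unadjusted and 27% adjusted, so adjustment does not improve it.

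**5. If ESR1 is prognostic only on tamoxifen.** Going from an even split to 3:7 then matters only through the tamoxifen arm, where the mutant share rises from 5/20 to 7/20. The factor is exp(−0.10·ln 2) = 0.93, against 0.87 in step 2. In simulation (g = 2 on tamoxifen, 1 on fulvestrant, no effect in wild type) the unadjusted HR moves from 0.86 over all splits to 0.81 at 3:7. Since ln(0.81/0.86) = −0.060 and ln 0.88 = −0.128, the shift is about half. P(HR < 0.8) is 48% unadjusted and 44% adjusted. The 0.86 here is a real average effect, because mutant patients do better on fulvestrant in this scenario.

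**6. Price of adjusting.** At g = 2 the SD of the log HR rises from about 0.36 to 0.37 averaged over splits, and from about 0.35 to 0.39 at 3:7.

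**The case against.** The strongest reply is that the rule performs no better overall once adjusted. The false promising rate stays near 26-27%, because it comes from few events and a rule without an interval. That is correct. A reader might infer that leaving ESR1 out inflates the trial's error rate; step 4 shows that it does not. What stands is the conditional argument: the team will interpret one trial with one known split, and given that split the unadjusted HR is displaced.

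A second reply is that section 1.1 itself says ESR1 mutation did not predict outcome on fulvestrant. This stands too. It halves the shift and makes any common-effect adjustment approximate.

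Third, PFS is secondary, the study is a pilot, and no stated action follows from the promising label. This limits the weight of the point but is no reason to leave the model open.

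Three other strong readings are tempting and lack support:

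- *The randomization is unstratified.* The documents name no factor, but they do not exclude one.
- *The plan ignores ESR1.* It has a separate rule for the mutant subgroup, which restricts on ESR1 presence already. It also reports mutation frequency by arm (11.1) and models circulating level over time. None of these adjusts the unselected HR.
- *Imbalance alone would produce a promising result.* At 7:3 the median HR stays at 0.84 or above for prognostic HRs up to 3. Of the cases examined, only 8:2 with a prognostic HR of 3 carries the median below 0.8 (to 0.77).

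**Conclusion.** The point holds as a cheap improvement to the PFS analysis. As written, the unselected HR has no stated protection against a chance imbalance in a factor the protocol reports as prognostic. An imbalance of 7:3 or worse has a 27% chance, about 14% in each direction. With no treatment effect, a prognostic HR of 2 and 34-35 events, the chance of a promising label is about 39% at one 7:3 split and about 16% at the reverse. It is about 27% at either split once ESR1 is accounted for.

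The probability of the split rests on the protocol's own prevalence. The size of the shift rests on an assumed prognostic HR and PFS distribution, and falls by about half if the mutation is not prognostic on fulvestrant. The gain is removal of the shift given the observed split, exact only if the treatment effect is the same in mutant and wild-type patients. It is not a lower overall false promising rate. The 0.65 rule for the mutant subgroup is unaffected.

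**What to change.** In 12.1, specify that the unselected-population PFS comparison is a Cox model stratified by baseline (pre-treatment) plasma ESR1 status, mutant or wild type. The time-varying level should not be used for this, because it is measured after treatment starts. State that the 0.8 criterion applies to the stratified HR, and report the unadjusted HR alongside. Read both next to the HR already planned for the mutant subgroup, since the treatment effect may differ by ESR1 status.

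The cost is one sentence and the small loss of precision shown above. No new sample, visit or patient is needed, and because the change is to the analysis, the assay result need not be available before allocation.

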1.2 Research hypothesis

1. In the 2nd to 3rd line of AI resistant WT ESR1 MBC, Fulvestrant plus palbociclib treatment will result in earlier detection of ESR1 mutations compared to treatment with tamoxifen plus palbociclib
2. In the 2nd to 3rd line of AI resistant mutant ESR1 MBC, Fulvestrant plus palbociclib will result in increased PFS compared with tamoxifen plus palbociclib
3. Change of allele frequency of ESR1 mutation is associated with PFS in all groups

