2. STUDY OBJECTIVES

2.1 Primary objective

1. Assessment of longitudinal changes in allele frequency of ESR1 mutation in plasma in patients treated with Fulvestrant plus palbociclib compared to tamoxifen plus palbociclib
2. Assessment of genomic alterations (using MammaSeq) associated with wildtype or mutant ESR1
3. Assessment of the functionality of ESR1 in tumor biopsies collected prior to and following treatment with fulvestrant plus palbociclib, or tamoxifen plus palbociclib, as assessed by RNAseq
4. Safety and toxicity assessment

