6.3 Efficacy

Response and progression will be evaluated in this study using the international criteria proposed by the revised Response Evaluation Criteria in Solid Tumours (RECIST) Committee (version 1.1). Changes in only the largest diameter (unidimensional measurement) of the tumor lesions are used in the RECIST criteria. Patients will be evaluated for response after every 2 cycles of therapy. In the case of non-measurable disease (as defined in 6.3.2), progression of disease will be determined by the appearance of new metastatic lesions or clinical worsening secondary to the non-measurable metastatic site at the treating physician's discretion.

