9. STUDY MANAGEMENT

9.1 TABLE 4. Study timetable and end of study

Procedure	Screening ^a	Visit 1	Every 4 weeks	Every 8 weeks	Off Treatment	Follow Up
INFORMED CONSENT	X					
CLINICAL ASSESSMENTS						
Physical Exam	X	X	X ^b		X	X ^c
Medical History	X	X				X ^c
Vital Signs, Height, Weight	X	X ^d	X		X	(X)
ECOG Performance Status	X	X	X		X	
LABORATORY TESTS:						
Hematology (CBC with diff, platelets)	X	X ^e	X ^f		(X)	
Chemistries and liver function tests ^g	X	X ^e	X ^f		(X)	
PT, INR, PTT ^q	X					
Estradiol ^h	X					
Pregnancy Test ⁱ	X			X		
IMAGING:						
CT Chest/Abd/Pelvis ^j	X ^j			X	(X)	(X)
Brain MRI	X ^k				(X)	(X)
TREATMENT:						
Tamoxifen		X ^L				
Fulvestrant		X	X ^L			
Palbociclib		X ^P				

OTHER ASSESSMENTS:						
Concomitant Medication Review	X	X	X		X	
Symptom/Toxicity Assessment	X	X	X		X ^m	
Follow-up/Survival					X ⁿ	X ^c
CORRELATIVE STUDIES						
Blood collection for ESR1-mt analyzed by ct-DNA	X		X		X	
Archived tissue sample (from breast primary)	X					
Optional Solid Tumor Biopsy	X ^o				X ^o	

- a) Screening assessments are required within 28 days of initiation of treatment unless otherwise noted.
- b) Required ≤ 1 day prior to each specified treatment (exceptions may be made to extend this window, with approval by the Protocol Chair/designee).
- c) To continue until patient death
- d) Height at baseline only
- e) Required ≤ 14 days prior to first day of treatment; baseline labs may be used if within window.
- f) Required ≤ 1 day prior to each specified treatment (exceptions may be made to extend this window, with approval by the Protocol Chair/designee).
- g) Chemistries to include measurement of sodium, potassium, chloride, CO₂, BUN, creatinine, glucose, total bilirubin, calcium, total protein, albumin, AST, ALT, and alkaline phosphatase.
- h) Estradiol if required to determine post-menopausal status can be performed any time prior to Visit 1 treatment
- i) Serum Pregnancy test is required for women of childbearing potential only. Required ≤ 7 days prior to first treatment (i.e., day 1) unless otherwise noted. All outcomes of pregnancy should be reported to the PI and AstraZeneca.
- j) PET/CT is allowed and the choice between using a CT or PET with CT will belong to the treating physician. If a PET is chosen, the CT is mandatory and must be of diagnostic quality.
- k) Only if known CNS metastasis

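### The first primary objective, longitudinal plasma ESR1 on fulvestrant versus tamoxifen, has no between-arm or time-to-detection analysis, and the one per-arm ESR1 output has no time point

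*Combined protocol and SAP*

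**What the plan says.** Section 2.1 gives as the first primary objective "Assessment of longitudinal changes in allele frequency of ESR1 mutation in plasma in patients treated with Fulvestrant plus palbociclib compared to tamoxifen plus palbociclib". Section 1.2 (Research hypothesis) states, for wild-type disease, that "Fulvestrant plus palbociclib treatment will result in earlier detection of ESR1 mutations compared to treatment with tamoxifen plus palbociclib". Both are comparisons between arms, and both concern time.

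The samples are scheduled. In section 3.1 "all patients will undergo ct-DNA ESR1 mutation evaluation every 28 days", and at progression "the last blood drawn for evaluation of ct-DNA ESR1-mt will occur". In Table 4 (section 9.1) the row "Blood collection for ESR1-mt analyzed by ct-DNA" is marked at screening, every 4 weeks and off treatment.

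Section 12.1 names treatment arm for PFS, response and adverse events. Its ESR1 analyses are:
- tissue-plasma agreement by kappa, with linear mixed models and the concordance correlation coefficient comparing variation between and within patients;
- an approach that "may also be applied to assessment of within-patient longitudinal change";
- presence and allele frequency of any ESR1 mutation, as the main correlative analysis;
- longitudinal change for specific mutations, as a secondary analysis;
- ESR1 level and change as predictors of PFS.

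Section 11.1 calls the primary objectives descriptive. It also says that the frequency of ESR1 mutation will be reported overall and in each treated cohort, from tumor and blood, with no time point.

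**The concern.** In none of the analyses in 12.1 is ESR1 the outcome and treatment arm a factor. None defines time to first detection, how progression ends it, or the set of patients without a mutation at baseline. Followed as written, the plan produces no arm comparison for its first primary objective.

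The nearest substitute is the per-arm frequency in 11.1. Its meaning depends on a time point that is not given, and on one natural reading it differs between arms whenever PFS differs, even if mutations emerge at the same rate. Section 12.2 justifies the trial by what it will tell future studies and mentions a between-arm difference in mutational evolution as a possible signal. The summary used to look for that signal would be chosen after the serial data are seen, in an open-label trial.

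**Working it through.** **Inputs from the documents.** 20 patients per arm (12.2). Expected plasma positivity 25% (6.3.5), which reproduces from the pilot counts in 1.1: 5/20 = 25%. So 20 × 0.25 = 5 baseline-positive and 15 baseline-negative patients per arm. The total of 40 is set by external constraints, so there is no power figure to reproduce.

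**Assumed inputs.** Constant emergence λ of 0.04 per month in both arms (range 0.02 to 0.08), independent of progression; tamoxifen-arm median PFS of 4 months (range 3 to 6); wild-type PFS hazard ratio (HR) of 0.8.

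**The 11.1 frequency, three readings.**
- *Baseline prevalence:* measured before treatment, so it holds no information on change.
- *Frequency by visit and arm:* partly describes detection over time, but it is a share of carriers, not an allele frequency, and it does not isolate baseline-negative patients.
- *Ever-detected:* quantified next. A draw at progression means that a mutation emerging before progression is found.

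**Ever-detected, baseline-negative patients, complete follow-up.** Share = λ/(λ+μ), with μ = (ln 2/median) × HR.
- Tamoxifen: μ = 0.1733; 0.04/0.2133 = 18.8%.
- Fulvestrant, HR 0.8: μ = 0.1386; 0.04/0.1786 = 22.4%.
- Spurious gap 3.6 points, or 0.036 × 15 = about 0.5 of a patient.
- Range at HR 0.8: 1.8 points (λ 0.02, median 3 months: 8.0% vs 9.8%) to 5.5 points (λ 0.08, median 6 months: 40.9% vs 46.4%).

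**Follow-up cut at 6 months.** Multiply by 1 − exp(−(λ+μ)t), t = 6: 13.5% vs 14.7%, a gap of 1.2 points. Section 12.1 allows analysis from 6 months after the last enrolment, so the actual gap would lie between 1.2 and 3.6 points, depending on accrual.

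**Milder wild-type PFS effect.** Section 12.1 calls fulvestrant promising at HR below 0.8 in all patients and below 0.65 in mutant disease. Taking these as true values and weighting log HRs by 75% and 25% (an approximation), the wild-type HR is exp[(ln 0.8 − 0.25 ln 0.65)/0.75] = 0.86. The complete-follow-up share is then 21.2%, a gap of 2.4 points.

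**Mixing old with new.** Over all patients, ever-detected is 25 + 0.75 × 18.8 = 39% vs 25 + 0.75 × 22.4 = 42%; 25 points in each arm were present at baseline.

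**Fixed cycles instead.** The 6-month formula gives 6.1% vs 6.3% after 2 cycles (1.84 months) and 13.0% vs 14.0% after 6 (5.52 months). The artefact nearly vanishes early and is about 1 point by cycle 6.

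**Precision of a hazard ratio for new detection.** Expected detections are 15 × 0.188 = 2.81 and 15 × 0.224 = 3.36. The 95% interval factor is exp(1.96 × √(1/2.81 + 1/3.36)) = about 4.9 either way. In 6,000 simulated trials of 15 per arm the median factor was 6.0, and 8.9% gave no estimate because an arm had no detection.

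**Dependence.** Hypothesis 3 says that "Change of allele frequency of ESR1 mutation is associated with PFS in all groups", so emergence and progression may be linked. In a simulation with one shared gamma frailty (variance 0.5 to 1) driving both, equal emergence gave a cause-specific HR of 1.05 to 1.09 at PFS HR 0.8.

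**Number of baseline-positive patients.** With Binomial(20, p) per arm, the chance that either arm has 3 or fewer is 1 − (1 − P(X ≤ 3))². It is 91% at p = 14%, 40% at 25%, 27% at 28% and 0.3% at 50%. All four prevalences appear in 1.1 or 6.3.5.

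**The case against.** The strongest reply is that this is a pilot, that 11.1 makes the primary objectives descriptive, and that the intent is clear: sections 1.1 and 1.2 (Rationale) speak of following plasma ESR1 over time on both therapies, and 12.2 names the between-arm signal. That removes any need for a formal test or for power. It does not say what will be described, and none of those passages attaches a method.

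Several stronger readings are tempting, and the documents do not support them.
- A reader might infer from "may also be applied to assessment of within-patient longitudinal change" that longitudinal analysis is optional altogether. The permissive verb concerns one method; 12.1 commits to longitudinal change for specific mutations.
- A reader might infer that the 11.1 frequency cannot bear on the objective at all. Read by visit, it would in part.
- A reader might apply the 0.65 threshold to wild-type patients, which would raise the fulvestrant share to 26.2%. In 12.1 that threshold belongs to the mutant subgroup; no passage gives it for wild-type disease.
- A reader might take the complete-follow-up gap as the expected bias. It is the upper end under the base-case assumptions.

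It is also fair to say that a hazard ratio on about six detections is weak and, if emergence and progression are linked, biased. That stands, and is why it should be an addition to the main summary and not the summary itself.

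**Conclusion.** The gap in the text is certain: no ESR1 analysis in 12.1 compares arms or defines time to detection, and the only per-arm ESR1 output lacks a time point. It should be fixed before the serial data are analysed.

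The numerical consequence is modest and conditional. It arises only if 11.1 is read as ever-detected. The direction is firmer than the size: with equal emergence, longer PFS on fulvestrant pushes the ever-detected share towards Hypothesis 1. The size rests on the assumed emergence rate, median PFS, wild-type hazard ratio, independence and length of follow-up. With about 15 baseline-negative patients per arm, no choice of summary will give a precise answer; the gain is that the objective is answered by a stated, interpretable one.

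**What to change.** In 12.1, name the between-arm plasma ESR1 comparison as the descriptive analysis of the first primary objective, split by pre-dose plasma status.

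- **Undetected at baseline:** cumulative incidence of new detection by arm at fixed cycles with 95% confidence intervals, treating progression or death as competing events. Cycles 2, 4 and 6 would fit, since "Patients will be evaluated for response after every 2 cycles of therapy", but others would serve. A cause-specific hazard ratio may be added, stating that it is imprecise (a factor of about 5 to 6 either way) and biased if emergence and progression are dependent.
- **Detected at baseline:** the linear mixed model already named in 12.1, applied to log allele frequency with arm, time and arm-by-time terms. If there are too few patients, show individual trajectories by arm, and set the minimum number in advance, because expected prevalence leaves it very uncertain.

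In 11.1, report baseline prevalence separately from new detection, each with its time point.

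The cost is SAP wording and a little more analysis work. Sample size and sampling stay as they are. The downside is wide intervals, and possibly trajectories only in the baseline-positive group.
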